Study Design and Duration

This is a randomized controlled study. Approximately 100 children, age 4 – 17 years, who are currently receiving subcutaneous immunotherapy, will randomly select a blinded envelope which assigns the distraction technique to be utilized during their study participation. There will be 25 envelopes assigned to each study group for a total of 100 envelopes. Each envelope will contain a paper with a colored sticker for the associated group assignment and number sequence.

The distribution of group assignment by number sequence and color is as follows:

- Interventional Groups
 1. Shot Blocker® # 1-25 (RED)
 2. Buzzy I (vibrating only) # 26-50 (GREEN)
 3. Buzzy II (vibrating and ice wings) # 51-75 (BLUE)
- Control Group
 4. Ethyl Chloride/Pain Ease Spray # 76-100 (YELLOW)

The three interventional groups are currently marketed distraction devices. The control group is the current clinical standard of care option for pre-allergy injection application.

The study consists of two visits. Both visits will be conducted during the participants routine clinic visit for allergy injections. At the first visit the investigator will assess eligibility. An overview of the study requirements will be provided to parent/child and consent/assent will be obtained.

During the second visit, the child will be randomized to a distraction technique or standard of care group to be utilized with the allergy injection(s) administered at this visit. Adherence with institutional allergy injection guidelines will be maintained. Prior to the application of the distraction method, the investigator will interview the parent to collect data related to demographic information and their child's current allergy health and treatment regime. The child's pain perception will be assessed before and after the allergy injection. The parent's perception of their child's pain will be assessed after the allergy injection. The investigator will provide information on the application of the randomized method and will provide instruction on the completion of the pain scales and questionnaires. The investigator and study staff will not indicate a method preference or guide the child or parent with their pain level responses. After completion of the second visit, the child's study participation is complete.

Inclusion & Exclusion Criteria

Inclusion Criteria

- Children aged 4-17 years on injection immunotherapy

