- A minimum of three allergy injection injections prior to enrollment at Visit 1

- Child accompanied by parent or legal guardian

Exclusion Criteria

- Children with a known pain or sensory disorders
- Developmental delays lacking necessary cognitive ability
- Administration of any form of pain analgesic within eight hours of randomization at Visit 2

Study Procedures

Visit 1:

Children aged 4-17 years who present to receive their injection(s) in the allergy clinic will be screened by the Principal Investigator or Co-Investigator for study inclusion and exclusion criteria. During their routine post-allergy injection 30-minute wait time, the investigator and the research coordinator will provide the parent and child with an overview of the study design, the risk and benefits assessment and study requirements. The investigator will advise the parent/child of the pain analgesic administration exclusion for the randomization visit. After obtaining parental permission and child assent, the child will be considered enrolled in the study. A subject ID will be assigned. A visible mark placed on the child's allergy injection chart will indicate the child is ready to be randomized at their next routine allergy injection visit.

Visit 2:

At a future allergy injection clinic visit the parent and the child will be asked if the child took any pain-relieving medicines, like Tylenol or Advil, within eight hours before coming to the clinic. If the participant needed this kind of medicine, the allergy shot appointment will be the same as before the study.

Study visit 2 will be completed at another routine allergy shot appointment. Preferably the next scheduled allergy injection visit.

If the participant did **not** take any pain relieving medicine within the previous eight hours, visit 2 will continue. The participants study group assignment will be determined. The envelopes identifying the four group assignments will be coded by number and color. The child will be presented with a basket containing all the envelopes. The investigator will instruct the child to select one envelope from the basket. The envelope selected at random by the child will determine the distraction method to be utilized prior to the allergy injection(s). The possible group assignments, one of three currently marketed distraction devices or the control group utilizing the current standard of care option, are listed below and are further detailed in Attachments I – III.

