Discontinuation and Replacement of study participants

A child has the right to withdraw from study participation prior to the completion of Visit 2. Early withdrawal participants will be replaced one to one.

Participant ID assignment

The study participants will receive a Participant ID at Visit 1 which will be used for all data collection. The Participant ID used will range from 001 to 100. If a study participant withdraws before the completion of Visit 2, the Participant and associated group assignment will be replaced. Replacement Participant ID's will be sequential beginning with the number 101.

Data Collection

Medication administration data collected will be limited to the participant's current immunotherapy vial and dosing, distraction method utilized, site of the application method and, if applicable, antihistamine use and pain medication use. Demographic data collected will be age, race and gender. Symptom and health data point collection will target allergy injection reactions and the presence of allergic rhinitis, asthma and atopic dermatitis. (Refer to Attachment V). Pain perception data will be collected from both the child and parent using facial and numeric pain scales (Refer to Attachment IV).

All data collected will be entered into an EXCEL data collection tool and stored on password protected, secure computers. The data will accessible only to the investigators and research coordinators in the study.

Data Analysis

Quantitative component data collected and evaluated for this study will include the number of patient participants within the allergy department, randomized interventions used, diagnoses including allergic rhinitis, asthma and atopic dermatitis, immunotherapy medication and dose, antihistamine and pain medication utilization, patient and parental pain scores, adverse reactions, age, race, and gender.

Quantitative component data collected for this study will be extracted into Microsoft Excel spreadsheets and analyzed using Excel functions. Target population demographic characteristics will be analyzed using descriptive statistics by the principal investigator with the level of significance set at <0.05.

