Face 0 doesn't hurt at all. Face 2 hurts just a little bit. Face 4 hurts a little bit more. Face 6 hurts even more. Face 8 hurt a whole lot. Face 10 hurts as much as you can imagine, although you don't have to be crying to have this worst pain.

Ask the person to choose the face that best depicts the pain they are experiencing.

Numeric Rating Scale

PAIN SCORE 0-10 NUMERICAL RATING

0-10 Numerical Rating Scale

0 1 2 3 4 5 6 7 8 9 10

No Pain Moderate Pain Worst Possible Pain

Instructions: Parent/ Guardian, please circle what pain level YOU percieve YOUR child to be in just after receiving their subcutaneous Immunotherapy (allergy shots).

PPAST v1.0-Numeric Rating Scale

V – Parent Questionnaire: Demographic – Health – Treatment Questionnaire

PPAST study Source Document Worksheet – Attachment V
PI: [name], MSN, APRN, PCNS-BC, CPEN

Participant ID: _____ Visit 2: ____/____/____

Demographic – Health – Treatment Questionnaire: Parent Interview

*Investigator will interview the parent to complete this questionnaire.
Questionnaire to be completed prior to administering allergy shot.*

1. How old is your child? _____
2. What race / ethnicity is your child? _____
3. What gender is your child? _____
4. How long has your child been on allergy shots? (Estimate in weeks, months or years) _____
5. What is the number of allergy shots your child will receive today? _____
6. What color vial is your child on? _____
7. What is your child's dose for the allergy shot? _____
8. What kind of allergy shot is your child receiving – venom / fire ant / environment? _____
9. Has your child ever had symptoms after receiving allergy shots? _____
If yes, explain: _____

10. Has your child taken any medication for pain today? _____
If yes: What was the name and dose of the pain medication? _____
For what reason was the medication given? _____
What time was the medication given? _____
11. Does your child use antihistamine medications? _____
If yes: What was the name and dose of this medication? _____
How often is the medication given? _____
What time was the medication given? _____
11. Please check the if your child has any of the following symptoms:

Allergic Rhinitis Asthma Atopic Dermatitis

Investigator Signature _____ : _____
Time form completed _____ / _____ / _____
Date form completed

V1.0 – 15Dec18

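### The plan's only significance level is attached to demographics, and no covariate is named for the four-arm pain comparison although age and pre-injection FACES are collected for every child

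*Combined protocol and SAP*

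**What the plan says.** The Objective is to compare techniques for reducing pain during allergy injections. Under Study Design and Duration, "There will be 25 envelopes assigned to each study group for a total of 100 envelopes". Under Visit 2, "The investigator will instruct the child to select one envelope from the basket"; no stratification by age is described. Eligibility covers "Children aged 4-17 years on injection immunotherapy".

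Two useful baseline variables are collected:

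- Age. Data Collection says "Demographic data collected will be age, race and gender", and item 1 of Attachment V asks the parent "How old is your child".
- Pre-injection pain. Study Design says "The child's pain perception will be assessed before and after the allergy injection".

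Data Analysis says the data will be "extracted into Microsoft Excel spreadsheets and analyzed using Excel functions". It lists age and the pain scores among the items to be evaluated. The sentence that carries the 0.05 level is about demographics: "Target population demographic characteristics will be analyzed using descriptive statistics by the principal investigator with the level of significance set at <0.05". The section names no test, model, contrast or covariate for the pain scores.

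**The concern.** The one inferential statement in the plan is attached to the variables that need it least. In a randomised trial, differences between arms in age, race or gender arise by chance. A p-value on them does not show whether an imbalance matters for pain, and the plan attaches no action to any result. A descriptive summary needs no significance level.

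The comparison that answers the objective has no level and no covariates. With 25 children per arm, ages from 4 to 17 and an unstratified draw, the arms can differ noticeably in age by chance. If self-rated pain varies with age, an analysis without age leaves that variation in the residual and leaves the realised imbalance in the estimated difference. Both can be reduced with data already on the forms. Covariates chosen after the arms have been seen invite selective adjustment, so the choice belongs in the plan.

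**Working it through.** The only sample-size figure that can be reproduced is 4 × 25 = 100. The documents give no effect size, power, age SD, pain SD or age-pain correlation, so the values below marked as assumed are not the plan's.

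**Inputs from the documents:** 25 per arm, four arms, ages 4-17, level 0.05.

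**Assumed:** age SD 4.03 (whole years spread evenly over 4-17), with 3.5 and 3.0 as alternatives; pain falling 0.1-0.3 points per year of age; pain SD 2.5-3.0 points.

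1. **Age SD if evenly spread.** There are 14 whole-year ages, so SD = √((14² − 1)/12) = √16.25 = 4.03.

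2. **SE of a difference in mean age between two arms.** SD × √(2/25) = 4.03 × 0.283 = 1.14 years. At SD 3.5 it is 0.99; at SD 3.0 it is 0.85.

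3. **Chance of an age gap of 2 years or more.**
   - SD 4.03: 2/1.14 = 1.75 SE, about 8% for one given pair. Simulation of four arms of 25 gives about 20% for at least one device against the spray and about 31% for at least one of the six pairs (30% from the studentized range).
   - SD 3.5: 4% for one pair, 18% for any of six.
   - SD 3.0: 2% for one pair, about 8-9% for any of six.

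4. **What a 2-year gap does to a pain contrast.** 2 × 0.1 to 2 × 0.3 = 0.2 to 0.6 points. The SE of an unadjusted two-arm pain difference is 2.5 × 0.283 = 0.71 to 3.0 × 0.283 = 0.85 points, so the shift is smaller than one SE.

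5. **Precision from adjusting for age.** Correlation r = slope × age SD / pain SD.
   - Lowest: 0.1 × 4.03/3.0 = 0.13. Highest: 0.3 × 4.03/2.5 = 0.48.
   - Adjustment cuts the variance by r²: about 2% to 23%.
   - Equivalent gain in children, 1/(1 − r²) − 1: about 2% to 31%.
   - At age SD 3.0 the same slopes give r = 0.1 × 3.0/3.0 = 0.10 to 0.3 × 3.0/2.5 = 0.36, a cut of about 1% to 13%.
   - At r = 0 the gain is nil.

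6. **The same in power.** For an assumed 2-point difference, pain SD 2.5, 25 per arm and two-sided 0.05, power for one pair is 80.7% unadjusted. It becomes 82.3% at r = 0.2, 84.3% at 0.3, 87.0% at 0.4 and 90.4% at 0.5.

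7. **Cost in degrees of freedom.** Four arm means leave 100 − 4 = 96 residual degrees of freedom. Two covariates leave 94.

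The extra gain from the pre-injection FACES score is not calculated, because the documents give nothing on its spread or its correlation with the post-injection score.

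**The case against.** The strongest reply is that randomisation already does the work. A chance age imbalance is part of what the unadjusted standard error allows for, so the unadjusted test is valid and the estimate unbiased on average. The assumed shift of 0.2-0.6 points is at most 30% of one 2-point FACES step. At correlations of 0.2-0.3 the power gain is only about 2-4 percentage points. All of this stands. The point concerns efficiency and chance imbalance in the one trial that will be run.

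A second reply is that the larger gap is the absence of any defined pain analysis, with covariates a refinement of that. This also stands, and the fix is written to supply both.

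Four stronger readings are tempting, and the documents do not support them.

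- A reader might infer that the plan prescribes an unadjusted comparison, or confines age to a demographic table. It prescribes no pain comparison of either kind, and it lists age with the pain scores among the data to be evaluated.
- A reader might infer that the plan tests age between arms and would pass a 2-year gap as balanced. No such test is written; the sentence speaks of descriptive statistics, and a misplaced significance level is at least as natural a reading. The result would also depend on the age SD: for two arms of 25, a 2-year gap gives p = 0.086 at SD 4.03, 0.049 at 3.5 and about 0.02 at 3.0.
- A reader might count many questionnaire items and infer a high rate of false flags. The section names three demographics. If each were tested independently at 0.05, the chance of at least one flag would be 1 − 0.95³ = 14%.
- A reader might infer systematic bias from the missing adjustment. Under a proper random draw there is none.

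**Conclusion.** The concern holds in a limited form. The 0.05 level sits on demographics, where it serves no purpose, and no covariate is named for the pain comparison even though two suitable ones are collected. The trial is not invalidated. The consequence is avoidable imprecision if age predicts pain, together with an uncorrected chance imbalance. An age gap of 2 years or more in at least one pair of arms has a probability of about 31% at age SD 4.0 and about 8-9% at 3.0. The variance saving is about 2-23% for correlations of 0.13-0.48 and zero if age and pain are unrelated. These figures rest on assumed spreads and slopes. The misplaced significance level and the missing covariates are matters of the text and rest on no assumption. Because the repair is nearly free, it should be made before any pain data are examined.

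**What to change.** Amend Data Analysis as follows.

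- Report age, race and gender by arm descriptively, without p-values.
- Move the 0.05 level (two-sided) to the pain contrasts. List those contrasts and say how the level is shared among them.
- Make the primary analysis a linear model of the child's post-injection FACES score on arm, age in years (continuous) and pre-injection FACES score.
- Analyse the parent's numeric score with the same model, as secondary.
- Report the unadjusted comparison and label it a sensitivity analysis, so that the choice between the two results is made in advance.
- State that the pre-injection FACES form is completed before the envelope is drawn. The protocol places it before any intervention but does not say whether it precedes the draw, and a covariate should not be open to influence from knowledge of the assignment.

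The downside is two degrees of freedom (96 to 94) and an analysis slightly more complex than a comparison of means. FACES has six levels, so the linear model is an approximation that estimates mean differences. No new data, visits or staff are needed. If neither covariate predicts pain, nothing is gained and almost nothing is lost.

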ShotBlocker is a novel application of the gate control theory of pain management. ShotBlocker is a flexible plastic disk that has a number of blunt contact points on its underside. When pressed firmly against the patient's skin at the injection site, ShotBlocker saturates the sensory signals distracting the patient from the pain signals caused by the needle poke.

How to Use

1. Select the injection site and prep the skin as usual.
2. Hold ShotBlocker so that the blunt contact points touch the patient's skin at the injection site.
3. Press ShotBlocker FIRMLY against the skin. (A)
DO NOT MOVE OR REMOVE SHOTBLOCKER UNTIL THE INJECTION HAS BEEN COMPLETED.
4. Immediately administer the injection in the usual manner through or near the central opening of ShotBlocker. For subcutaneous injections, angle the needle as needed to give the injection. (B)
IF MORE THAN 20 SECONDS ELAPSE BETWEEN THE PLACEMENT OF SHOTBLOCKER AND THE INJECTION, COMPLETELY REMOVE SHOTBLOCKER FROM THE SKIN. REPEAT THE PROCESS BEGINNING WITH STEP 2.
5. After you have completed the injection and withdrawn the needle, remove and discard ShotBlocker.

U.S. Patent #6,902,554
© 2012 Bionix Medical Technologies.

[name]
[contact] • [contact]
www.BionixMed.com

II – Buzzy Bee I (*with ice pack-wings*) and Buzzy Bee II (*without ice pack-wings*)

Developed by a physician, Buzzy® is a reusable device for minor aches and pains.

Buzzy® is a personal consumer use product intended to be used by a single user.

Bring with you to the doctor, or use at home for:

- STINGS
- SPLINTERS
- SHOTS

BuzzyHelps.com

Home Use Rev. 02.01.17

ICE WINGS:

Wings will stay frozen 10 minutes at room temperature. For best pain relief, the Wings must be frozen solid to avoid absorbing vibration.

Face the blue or smooth side of the Wings toward the skin for more numbing power. If sensitive to cold, the soft side of the wings should face the skin.

Tip: For long procedures or for medications that burn or sting, prepare additional Wings.

Store folded Wings in freezer. Gel inside Wings is a non-toxic, safe, food-grade product that may deteriorate if not stored properly.

Note: To transport, place the Wings between the ColdToGo bag blue ice inserts (sold separately), or between 2 commercial cold packs (sold separately) to maintain frozen temperature.

COMFORT STRAP:

Our Comfort Strap is a reusable, single-handed tourniquet, smooth and pinch free. To use, 1. Loop the Comfort Strap around the arm, passing one end through the slit in the other. 2. Hold the slit and pull the other end through until the desired tension is reached, then release the slit end. 3. To lock the Comfort Strap in position, release the tension from the long end. 4. To release, simply pull gently on the short end and the Comfort Strap will fall away.

For shots: Switch on to activate the vibration, and then place Buzzy® on the site of the shot. Leave for 15 seconds for surface shots – 60 seconds for deeper injections. Immediately before cleaning the site, move Buzzy® proximal (closer to the head) to the pain location, and press in place throughout cleaning and getting the shot.

For children who get their shots sitting up, a parent can put an arm around the shoulders to hold Buzzy® for them.

INDICATIONS FOR USE	1
CONTRAINDICATIONS, WARNINGS, AND CAUTIONS	1
ICE WINGS	2
COMFORT STRAP	2
DIRECTIONS FOR USE	3
BUZZY PLACEMENT	4
SHOTS	5
STOMACH INJECTIONS	6
FOR ACHEs AND PAINS	6
FINGER STICKS, SPLINTERS	7
BURNING, ITCHING	7
IVs AND PHLEBOTOMY	8
CLEANING, CHANGING BATTERIES, TROUBLESHOOTING, ORDERING, GUARANTEE	10

DIRECTIONS FOR USE:

Immediately before use, remove the Wings from the freezer and attach behind Buzzy® on the hook. Activate by firmly pressing button on top of Buzzy®. Press a second time to turn Buzzy® off.

Buzzy® has an energy saving automatic shut-off after 3 minutes of constant use. Simply press the button on top of Buzzy® to reactivate vibration.

Buzzy comes with a silicone Comfort Strap to hold Buzzy in place on extremities. 1. Loop the Comfort Strap around the arm, passing one end through the slit in the other. 2. Hold the slit and pull the other end through until the desired tension is reached, then release the slit end. 3. To lock the Comfort Strap in position, release the tension from the long end. 4. To release, simply pull gently on the short end and the Comfort Strap will fall away.

Use Buzzy® only on clean, unbroken skin. The stripes on Buzzy®, or bottom end should be closest to the procedure, and the head on Buzzy® and switch farthest away.

Tip: For best results, center the bigger rounded end of Buzzy® directly next to the pain.

INDICATIONS FOR USE:

Controls pain associated with injections (venipuncture, IV starts, cosmetic procedures) and the temporary relief of minor injuries (muscle or tendon aches, splinters and bee stings). Also intended to treat myofascial pain caused by trigger points, restricted motion and muscle tension.

Fold Wings and STORE IN FREEZER. Wings must be frozen solid for best effects. Personal Buzzy® units come with universal personal Ice Wings & Comfort Strap.

WARNINGS: For intended use only • Direct or prolonged application of ice could vasoconstrict or alter lab values.

CONTRAINDICATIONS: Do not use in the presence of unexplained calf pain. Consult a physician. • This device should not be used over swollen or inflamed areas or skin eruptions. • Do not place directly on a thermal burn. • Do not use ice pack with underlying sensitivities to ice or cold (e.g. Sickle Cell Disease, Raynaud's Disease).

CAUTIONS: Store in a cool, dry place.

1

Buzzy PLACEMENT:

The Buzzy® physiologic blockade works best when placed "between the brain and the pain" in the same nerve area as the pain. On arms and shoulders, nerves run from fingers to shoulders to the spine. For the chest or back, the nerves run from the center of the chest or stomach horizontally to the back. On the thighs, the nerves run diagonally from the inner thigh around to the back to the spine.

For children: For best results, let children hold Buzzy® in advance for familiarity, and let them choose whether or not to use the ice pack.

4

For injections in the stomach:
Place Buzzy® lateral to the shot (i.e., belly button, the shot, and then Buzzy®).

Patent Pending Buzzy® is shown during an injection in the abdomen.

For Aches and Pains:

Apply directly to sore muscles for maximum of 10 minutes. Hold in place or attach with strap. Buzzy® has an energy saving automatic shut-off after 3 minutes of constant use. Simply press the button on top of Buzzy® to reactivate vibration.

For additional placement information, please visit: buzzy.hi/howto

For finger sticks or splinter removal: Switch on to activate the vibration, and then press Buzzy® on the palm with the bottom end toward the finger. Leave in place throughout cleaning and doing the procedure.

For burning or itching: like any cold and warm therapy application, Buzzy® can be helpful for burning or itching. For insect bites or medications that cause burning or itching, take frozen Wings and massage the vibrating Buzzy®/Wings combination directly on the site. Rub or press in place until the area feels better. Do not place Buzzy® directly on a thermal burn.

7

TROUBLESHOOTING:

When used with care, Buzzy® should last years. If Buzzy® is dropped repeatedly, however, the metal that holds the batteries in place can bend. If Buzzy® fails to function after a fall, try pinching battery clip in to restore contact.

HOW TO ORDER /ADDITIONAL INFORMATION:
Please visit our website BuzzyHelps.com for a complete list of FAQs, other pain management tips, how-to videos, accessories, replacement parts, and more!

GUARANTEE:

Previous medical history and intrinsic physiologic differences may make Buzzy® less effective for some people. If not completely satisfied, return within three months to place of purchase for a full refund, or contact us at the address below.

MANUFACTURER:
[name]
[name]
BuzzyHelps.com [contact]
[contact]

US Patented British Patent No. 2,455,695

RM-1910, 1248-004-500200, 1248-004-500100

Authorized European Representative:
M2 INTERNATIONAL S.A.
[name]
[name]
[contact] | www.epczz.com

Type B Applied Part

10

For IVs or phlebotomy:

Switch on to activate the vibration, and then place Buzzy® proximal (above) to the pain location. Press in place or tuck under tourniquet before immediately cleaning and obtaining access. Pass any tourniquet through slot to secure Buzzy® to arm. Do not put directly on site of access.

BATTERIES:
Buzzy's batteries will last at full strength about 20 hours. For best pain relief, replace batteries when vibration weakens. Unscrew the back using a Phillips head screwdriver to remove back panel. Buzzy® is powered by 2 alkaline AAA batteries. Remove batteries if Buzzy is not being used for extended period of time.

If you are having trouble powering on your Buzzy® unit, please open up your Buzzy®, remove the batteries, bend the battery tabs inward, and replace the batteries.

8

9

III – Ethyl chloride spray

Rx only
Invert the bottle while spraying.

